8.5.3 Follow-up assessments (cross-over between study arms occurs at 24±4 weeks)

Patients device makes 3 monthly transmissions via telephone line to a) ensure device functioning appropriately. (SC)

Patients return for follow-up examination after 24±4 weeks (Cross over b) testing) and 48±4 weeks (End of trial testing) by a blinded research team member. Symptomatic assessment performed with SF36 and Kansas City Cardiomyopathy questionnaires and determination of New York Heart Association (NYHA) functional class. (RES)

Patients will be asked if their symptoms have become less severe, stayed the same, or worsened.

Cardiopulmonary exercise testing (CPET) with concomitant TTE at 24±4 c) weeks and 48±4 weeks follow-up. (RES)

6 minute walk test for the assessment of exercise tolerance at 24±4 d) weeks and 48±4 weeks follow-up. (RES)

Venous blood sample taken at 24±4 weeks and 48±4 weeks. (RES) e)

8.6 Description of Assessments

8.6.1 History, physical examination and recording of prior test results

Patients will be asked to attend for initial assessment with physical examination and history taking.

8.6.2 12 lead ECG

A 12-lead ECG will be performed at baseline assessment and each clinical visit as standard care.

8.6.3 Transthoracic echocardiography

Comprehensive resting transthoracic echocardiography will be performed in accordance with European guidelines for the assessment of HCM⁴ and the latest British Society recommendations.²²

8.6.4 Cardiopulmonary exercise testing with concomitant TTE

Symptom limited cardiopulmonary exercise testing (CPET) will be performed in accordance with joint European and American guidelines.²³

8.6.5 Blood sample collection

A small blood sample (<5mL) will be taken from the participant at each visit. Blood will be taken by needle from a vein in the participant's arm by a nurse or member of the research team trained to do so. The blood sample will be analysed at the local pathology lab for levels of N terminal pro B type natriuretic peptide (BNP).

8.6.6 6 minute walk test

A six minute walk test will be performed in accordance with the American Thoracic Society guidelines.²⁴

8.6.7 Invasive haemodynamic pacing study in patient requiring PPM +/- ICD implant (SC)

a) Arterial access will be obtained by the Seldinger Technique from the right femoral artery (RFA) using a standard 7 French sheath. Venous access will be similarly obtained from the left subclavian or cephalic veins. The right atrial and right ventricular leads will be implanted as usual.

b) The coronary sinus will be intubated using a LV lead delivery guiding catheter. When necessary, coronary venous anatomy will be defined by balloon occlusion coronary sinus venography. The coronary veins will then be intubated with a deflectable quadripolar catheter or an angioplasty wire.

Intravenous heparin 5,000 units will be administered and the C) haemodynamic study performed. The LV apical pressures will be

measured with an end-hole pigtail catheter. The arterial pressure will be measured from the side arm of the RFA sheath. The pressure difference between LV and arterial pressures will be the mid-cavity gradient.

AV synchronous pacing will be performed from the right d) ventricular apex, right ventricular outflow tract, distal middle cardiac vein and posterior or lateral cardiac veins whilst measuring the respective LV gradients for 30 seconds before, during and after cessation of pacing.

If the best gradient reduction is achieved with LV pacing, a LV e) lead will be implanted with a biventricular device at the same sitting.

f) Following removal of the LV pigtail catheter, the activated clotting time will be checked. If it is more than 150 seconds, the heparin will be reversed with intravenous protamine sulphate.

g) The device will be programmed with the longest AV delay to allow continuous right or left ventricular pacing.

8.6.8 Invasive haemodynamic pacing study in patient with no other PPM +/- ICD indication or with an implanted dual chamber device (SC)

a) Arterial access will be obtained by the Seldinger Technique from the right femoral artery (RFA) using a standard 7 French sheath. Venous access will be similarly obtained from either the right femoral vein using two standard 7 French sheaths, or from the right femoral and right subclavian (assuming left sided device insitu) veins (depending upon the operator).

b) A quadripolar pacing catheter will be placed in the right atrial appendage. The coronary sinus will be intubated using a LV lead delivery guiding catheter. When necessary, coronary venous anatomy will be defined by balloon occlusion coronary sinus venography. The coronary veins will then be intubated with a deflectable quadripolar catheter or an angioplasty wire.

c) Intravenous heparin 5,000 units will be administered and the haemodynamic study performed. The LV apical pressures will be measured with an end-hole pigtail catheter. The arterial pressure will be measured from the side arm of the RFA sheath. The pressure difference between LV and arterial pressures will be the mid-cavity gradient.

d) AV synchronous pacing will be performed from the right ventricular apex, right ventricular outflow tract, distal middle cardiac vein and posterior or lateral cardiac veins whilst measuring the respective LV gradients for 30 seconds before, during and after cessation of pacing.

If the pacing study demonstrates significant mid-cavity gradient, e) the appropriate pacemaker will be implanted on the same or following day. If no mid-cavity gradient is demonstrable, the patient will not be suitable for the research study. A more conventional device will still be implanted if there are other indications. The more conventional device will almost always be one without the additional LV lead.

8.7 Discontinuation/Withdrawal of Participants from Study

Patients will be free to withdraw from the study at any point.

8.8 Procedure for Collecting Data Including Case Report Forms (CRFs) and storage

All source data will be collected by the investigator or a research nurse on paper CRFs, and data will be captured into the trial database (electronic data capture system) with electronic signatures and audit trail. All source data and CRFs will be kept securely in participant folders or the Trial Master File, which will be kept in a locked cupboard with restricted access in the Research Department.

8.9 Definition of End of Study

The end of the study is the last assessment of the last patient after 1 year of cross-over treatment and non-treatment arms (6 months of each).

| | Visit 1 | Visit 2 | Visit 3 | | Visit 4 |
|---|---------------------------|---------|----------------------------------|----------------|----------------------------------|
| Procedure | Pre-implant assessment | Implant | 24±4 weeks post implant | Cross- over | 48±4 weeks post implant |
| NYHA classification | x | | X | | X |
| SF36 & KCCM Questionnaire | x | | X | | X |
| CMR with stress perfusion | X | | | | |
| 6MW test | X | | X | | X |
| CPET with concomitant TTE | x | | X | | X |
| Randomisation | | x | | | |
| Device interrogation and programming at pacing clinic | | x | X | | X |
| Blood sample for BNP analysis | X | | X | | X |

8.10 Schedule of Assessment

9. STATISTICAL CONSIDERATIONS

9.1 Sample size calculation

<<Version 9>> <<09/11/2017>> <<Pacemaker therapy for drug-refractory symptoms in mid-cavity HCM

Effect size was calculated using our pilot work, where a reduction in midcavity gradient with distal ventricular pacing of around 60 mmHg was seen acutely, with a standard deviation of 26 mmHg. A clinically significant gradient reduction is 30 mmHg. Using a conservative approach, we aim to be able to detect a reduction of 25 mmHg. The magnitude of patient's resting gradients will be taken into consideration and accounted for during analysis. With two sided alpha level set at 0.05 a priori, and a power of 90%, the calculated sample size using a paired sample t-test was 15 to detect a 25mmHg acute reduction in gradient. In order to account for potential withdrawals from the study, the sample size has been increased to 25.

9.2 Statistical analysis

All patients completing the initial invasive pacing study will be eligible for the primary analysis. The secondary aim is to collect descriptive data regarding the feasibility of a cross-over design trial and corresponding methods used to assess symptoms and physical performance in this cohort. A statistical analysis of the results will be undertaken at the completion of the study by a senior statistician of the Cardiovascular Clinical Trials Unit. Descriptive statistics will be collected in the form of mean ± standard deviations, and these outputs will form the statistical basis for a larger multi-centre RCT.

| Delta | SD | Sig. | Power | Туре | Alternative | Sample size |
|-------|----|------|-------|--------|-------------|----------------|
| 30 | 26 | 0.05 | 0.8 | Paired | Two-sided | 9 |
| 25 | 26 | 0.05 | 0.8 | Paired | Two-sided | 10 |
| 20 | 26 | 0.05 | 0.8 | Paired | Two-sided | 16 |
| 25 | 26 | 0.05 | 0.9 | Paired | Two-sided | 15 |
| 20 | 26 | 0.05 | 0.9 | Paired | Two-sided | 20 |

Table 3: Sensitivity analysis table.

10. ETHICS

<<<<09/11/2017>> <<Pacemaker therapy for drug-refractory symptoms in mid-cavity HCM >>

Whilst we do not believe the study raises significant ethical issues, we have considered several ethical practicalities.

The treatments for patients with hypertrophic cardiomyopathy and mid-cavity obstruction to blood flow are very limited, but include medicines and cardiac transplant. The use of a pacemaker is an experimental treatment which has not yet been explored in a formal clinical trial.

We do not know which treatment method is generally better, which is why we are conducting the study. Participants will experience both a treatment period (pacing all the time) and a non-treatment period (very little pacing), before comparison of patient experience in both settings. The order in which the participant experiences each setting is not decided by their doctor or the research team, but by randomly assigning you to one or other first, like tossing a coin. Setting the pacemaker to pace all the time or pace very little will not affect the defibrillator function of the participant's device if it has one.

We have designed a clear and concise patient information sheet to explain this to prospective study participants, allowing them to make an informed choice as to whether to take part.

Another potential issue that the study raises is common to all cross-over design studies. If a participant has been randomised to be in the treatment arm first, and feels better (as we expect), and then switches to the nontreatment arm and feels symptomatically worse, they may not wish to continue the non-treatment arm. Because we don't know whether patients feel better due to the pacemaker setting, or simply just because they have undergone a procedure (placebo effect), it is necessary for the research participants to "cross-over" from one setting (treatment) to the other (nontreatment). Whilst this could be interpreted as withholding treatment from a patient, it should be stressed that it is not known whether one setting provides a benefit to the patient over another (when the patient is unaware of their treatment to mitigate against placebo effect).

Cross-over design studies are often considered the 'gold-standard' of medical research; however they are at risk of statistical impracticalities due to their

design. For example, if all patients randomised to the treatment arm first, decided they were not willing to stay on the non-treatment arm after switching (they will be shielded to pacemaker settings), then we will be unable to make the comparison between the two pacemaker settings in those patients. This outcome still provides useful information about the feasibility of cross-over design, and will infer that patients really do feel better when the pacemaker is set to work almost all the time.

However, it makes it difficult to make the comparison using the patient as their own control, as a comparison can only be made to the test scores before the device was implanted, and therefore cannot account for the placebo effect of device implantation alone regardless of settings.

It is important to note that the primary outcome is not affected by the ability of the patient to complete both arms of the cross-over, as this data is collected before randomisation occurs.

11.SAFETY CONSIDERATIONS:

A trial Data Safety Monitoring Committee (DSMC) will be formed to review the safety of the trial every 4 patients that are recruited and undergo invasive haemodynamic pacing study and device implant. The safety committee shall consist of an independent chairman, a cardiac device specialist, a cardiomyopathy doctor, and a clinical trialist. The CI ([name]), PhD student ([name]) will also be in attendance.

Participants do not receive exposure to higher doses of ionising radiation as part of this study.

The extra tests performed as part of the research, such as exercise stress echocardiography and 6-minute walk test are safe with very low risk to the participants.

12. DATA HANDLING AND RECORD KEEPING:

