8.4 Randomisation, blinding and code-breaking

A trial randomisation service (such as https://www.sealedenvelope.com or www.randomize.net) will be used to assign participants to one of the cross over arms initially.

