8.5 Baseline Assessments

8.5.1 Pre-pacing study assessment (several of these tests are standard pre-device implant care, denoted by SC. Research activity denoted by RES)

a) Symptomatic assessment with SF36 and Kansas City Cardiomyopathy questionnaires and determination of New York Heart Association (NYHA) functional class. (RES)

b) Venous blood sample taken (SC), BNP test (RES)

6 minute walk test (6MWT) performed to assess baseline exercise C) tolerance. (SC)

<< Version 9>> << 09/11/2017>> << Pacemaker therapy for drug-refractory symptoms in mid-cavity HCM >>

d) Resting comprehensive transthoracic echocardiographic (TTE) study. (SC)

Cardiopulmonary exercise testing (CPET) with concomitant TTE. (SC) e)

f) Cardiac Magnetic Resonance Imaging (CMR). (SC)

8.5.2 Invasive pacing study (standard care denoted by SC, research activity denoted by RES)

a) Haemodynamic study performed for maximal pressure gradient across the mid-cavity with and without pacing from the RV apex, left middle cardiac vein, or both, sequentially. (SC)

b) For patients judged to be at significantly increased risk of sudden cardiac death, they will have a device with defibrillator functions as well as the pacemaker functions. Those thought not to be at significantly increased risk of sudden cardiac death may have a device with pacemaker functions only. PPM +/- ICD inserted at optimal settings of AV delay and lead polarity. (SC)

After one-day check as an inpatient to ensure proper PPM +/- ICD c) function, patient randomised in a double-blind, cross-over fashion. In one arm, the device will be set to the pacing mode "AAI", which is a backup pacing mode at 30 beats per minute, so it will therefore not be activated (non-active pacing). In the other, the device will be set to the pacing mode "DDD", with optimal atrio-ventricular delay as assessed during invasive haemodynamic study. This means it will pace almost all of the time (active pacing). Simultaneous Doppler echocardiography will be used to ensure the atrial component of LV filling is not truncated. (RES)

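### Section 10 reads drop-out in one sequence as benefit from pacing, and overlooks the blinded, randomised week-24 comparison that such drop-out leaves intact

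*Protocol*

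**What the plan says.** Protocol 8.5.2(c) has each "patient randomised in a double-blind, cross-over fashion" after implant and a one-day device check. One setting is active DDD pacing; the other is AAI backup at 30 beats per minute, described as non-active. Under 8.4 a randomisation service "will be used to assign participants to one of the cross over arms initially", and Section 10 describes the order as set "by randomly assigning you to one or other first, like tossing a coin". Section 8.5.3 and the Schedule of Assessment place NYHA class, SF36, the Kansas City questionnaire, CPET with echocardiography, the walk test and a blood sample at 24±4 weeks, before the switch, with follow-up by a blinded team member.

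Section 10 then supposes that all active-first patients refuse to continue once switched to backup. It makes three statements about that case:

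- "then we will be unable to make the comparison between the two pacemaker settings in those patients".
- The outcome "will infer that patients really do feel better when the pacemaker is set to work almost all the time".
- With the patient as own control, "a comparison can only be made to the test scores before the device was implanted, and therefore cannot account for the placebo effect" of the implant itself.

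Section 8.7 adds only that "Patients will be free to withdraw from the study at any point". Section 9.2 treats the cross-over data as descriptive feasibility data that will form the statistical basis for a larger trial.

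**The concern.** Two things are unsatisfactory in the Section 10 passage.

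First, the only remaining comparator it names is the patient's own score before implant, which it acknowledges is confounded with placebo. The design supplies a better one. At week 24 both randomised groups have had the same procedure and differ by allocation only in the setting. A refusal that follows the switch comes after that visit.

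Second, it draws an efficacy conclusion from drop-out in one sequence. The passage of time, trial fatigue and a fading placebo response to implantation would also make patients leave in period 2, whichever setting they had first. Only drop-out in the backup-first sequence shows how much of the leaving such causes explain, and the passage does not mention it.

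The cross-over exists to test feasibility and to feed the design of a larger trial. Read as written, heavy drop-out, which is a feasibility failure, could be reported as a sign of benefit. Before-after changes inflated by placebo could also be carried into the next trial's assumptions. Section 10 itself foresees patients feeling worse after the switch, so the case is not remote.

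**Working it through.** **Plan's own figures.** The protocol gives no figure for cross-over drop-out or for the week-24 contrast. Its sample size (Section 9.1) is for the acute gradient: 15 for 25 mmHg, SD 26 mmHg, two-sided 0.05 and 90% power. An exact paired t calculation gives 14 (power 91.3%; 93.3% at 15), so the figure reproduces within one patient. It matters here only because it leads to the enrolled total of 25.

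**Assumption.** The allocation ratio is not stated. From the coin-toss description I take 12 active-first and 13 backup-first.

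**1. What drop-out in one sequence can show.** Take the protocol's own scenario: 12/12 active-first leave, and k of 13 backup-first leave. All s = 13 − k patients who stay are then backup-first. For the rows with k from 3 to 10, the two-sided Fisher p is [C(13,s) + C(12,s)] / C(25,s).

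| Backup-first leaving | s | Calculation | p |
|---|---|---|---|
| 3/13 | 10 | (286 + 66) / 3,268,760 | 0.0001 |
| 8/13 | 5 | (1,287 + 792) / 53,130 | 0.039 |
| 9/13 | 4 | (715 + 495) / 12,650 | 0.096 |
| 10/13 | 3 | (286 + 220) / 2,300 | 0.22 |
| 13/13 | 0 | no patient stays | 1.00 |

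Section 10 draws the same conclusion in every row.

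**2. What the week-24 contrast offers.** In units of the outcome's SD:

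- SE = √(1/12 + 1/13) = √0.1603 = 0.40.
- 95% CI half-width = t(0.975, 23) × SE = 2.069 × 0.400 = 0.83.
- Detectable difference at 80% power is 1.17 SD. Power is 22% at 0.5 SD and 48% at 0.8 SD.
- If only 15 patients reach week 24 (7 v 8): SE = √(1/7 + 1/8) = 0.52, half-width 2.160 × 0.518 = 1.12.

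Baseline adjustment multiplies the SE by √(1 − r²), where r is the correlation between baseline and week 24. The documents give no r. For r = 0.3, 0.5 and 0.7 the SE is 0.400 × 0.954 = 0.38, 0.400 × 0.866 = 0.35 and 0.400 × 0.714 = 0.29.

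**3. What is lost when period 2 is missing.** With all 25 patients complete, the SD of the within-patient difference is √(2(1 − ρ)). At 80% power the cross-over would detect 0.69, 0.58 or 0.45 SD for an assumed ρ of 0.3, 0.5 or 0.7. The week-24 contrast is therefore a much weaker instrument, but it is free of implant placebo.

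**The case against.** A reader might infer that the protocol is simply wrong to say only pre-implant scores remain. The text does not support that. The sentence is about using the patient as own control, and the related one is confined to the patients who leave. For someone with no period 2 data, the only other within-patient comparator is the pre-implant score, and it is confounded as stated. The fault is that the between-group comparison is left out.

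A reader might also infer that the plan commits itself to a before-after fallback analysis. It does not. The passage is a hypothetical in the ethics section, it presents the before-after comparison as a limitation, and week-24 data are scheduled for every patient. The model for incomplete cross-over data may properly be left to the SAP.

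Nor is the drop-out inference shown to be false. Patients are shielded from the settings, and the scenario is that all active-first patients leave. On the assumed split the excess over backup-first stays significant up to 8/13 and is lost from 9/13. A clear excess would be some evidence of an effect of setting. What remains is that the passage draws the conclusion without asking for that comparison, and that it sits badly with the next paragraph's admission that placebo cannot be accounted for.

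Finally, the passage itself notes that the primary endpoint is collected before randomisation. That stands and limits the consequences.

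**Conclusion.** The point holds as an omission and an unsupported inference. Section 10 overlooks the blinded, randomised week-24 comparison, which controls for implant placebo and survives later drop-out. It also treats drop-out in one sequence as evidence of benefit when its meaning depends on the other sequence: p runs from 0.0001 to 1.00 as backup-first drop-out goes from 3/13 to 13/13.

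The remedy should not be oversold. With an SE of about 0.40 SD and a CI half-width of about 0.83 SD unadjusted, the week-24 contrast can only be descriptive. These figures assume a 12 v 13 split and attendance of all 25 patients at week 24. Freedom from placebo bias also assumes that blinding holds to that visit. The primary endpoint and the sample size are unaffected.

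**What to change.** Change the wording of Section 10, with a matching sentence in 9.2:

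1. Replace the statement about what drop-out would show. Say that drop-out is feasibility information, to be reported by sequence and period with reasons, and that it supports an effect of setting only through the difference between the two sequences.
2. State that week-24 outcomes will be summarised by randomised group, adjusted for baseline, with a confidence interval, and that this is the placebo-controlled comparison if period 2 is largely missing. Say that it is descriptive.

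The model for the cross-over data can stay with the SAP. The outcome data are already scheduled, and no visit or sample-size change is needed. Reasons for leaving should be recorded where patients give them, since consent under 8.3 does not oblige them to. The cost is an edit to the text. The one drawback is that the named comparison is imprecise, which the confidence interval will make plain.

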12.1 Confidentiality

>>

<<Version 9>> <<09/11/2017>> <<Pacemaker therapy for drug-refractory symptoms in mid-cavity HCM

All patient information held is bound by the Confidentiality Code of Practice. Access will be on a strict need-to-know basis, with patient information only being shared with those involved in that patient's care. All patients' identifiable details will be anonymised from all study documentation (apart from their original case file) and they will be kept in participant study files in a locked cupboard in a pass protected room within the Research Department. Information related to participants will be kept confidential and managed in accordance with the Data Protection Act, NHS Caldecott Principles, The Research Governance Framework for Health and Social Care, and the conditions of Research Ethics Committee Approval. All research team members have undergone Good Clinical Practice Training.

